In addition to specific assays described above, whole blood, serum and plasma samples will be stored for future analysis that may include genetic determinants of antiplatelet drugs response, alternative mRNAs, and biomarkers.

Study endpoints, sample size calculation and statistical analysis

The primary end point of the study will be the non-inferiority in PRU measured at 2 hours after discontinuation of cangrelor vs. placebo. We hypothesize that in patient receiving

cangrelor following a ticagrelor LD platelet inhibition assessed by PRU will be non-inferior compared to patients receiving ticagrelor LD followed by placebo infusion. Non-inferiority will be assessed using a 95% confidence interval (CI) of the difference in mean PRU between the two arms. Under the assumption of 0 difference in mean PRU between group 1 and group 2 and a common standard deviation of 75 PRU, a sample size of 16 patients will allow for the 95% CI to stay within ± 45 PRU with a 95% power and alpha=0.05. Considering a 25% data attrition rate due to hemolysis, drop out or technical problems, 20 patients will need to be randomized in order to ensure complete available data for analysis. The sample size of this study was established according to results of previous PD investigations [18,30]. In line with previously reported investigations, 45 PRU was chosen for the noninferiority margin for the upper 95% CI limit of the difference [25, 31]. All other end points will be considered exploratory and will include the comparisons of PD and PK parameters, and P2Y₁₂ gene receptor level expression between all treatment arms at each time points, as well as the comparisons of rates of high on-treatment platelet reactivity (HPR). HPR will be defined as PRU>208, PRI>50%, and LTA-ADP>59%, in line with consensus definitions [32].

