Subjects will be identified with a number and data collection sheets will all be stored in a locked area. Data will be kept for 6 years after enrollment ends to comply with HIPAA regulations. Patients will receive a handout with the names and telephone numbers of the doctors involved in the study. Study subjects will be identified first (months 1-8): we expect to randomize 2-3 subjects monthly and complete enrollment in 8 months (total: 20 subjects

randomized). Months 9 and 10 will be implied for statistical analysis and manuscript preparation. Results will be presented at the first available major cardiovascular meeting (e.g. AHA, ACC, ESC), and final manuscript will be submitted to publication to one of major cardiovascular journals (e.g. JACC, Circulation, European Heart Journal).

Possible Discomforts and Risk

In clinical trials, the most common clinical side effect of cangrelor was bleeding. Severe/moderate bleeding occurred in 0.8% of patients receiving cangrelor, as compared to 0.6% of those receiving placebo; other side effects include dyspnea (1.3%), worsening renal function (3.2% of patients with severe renal impairment), and hypersensitivity (0.05%) [5]. In clinical trials, the most common clinical side effects of ticagrelor were dyspnea (13.8%), headache (6.5%), cough (4.9%), dizziness (4.5%), nausea (4.3%), and bradycardia (4.4%) principally. Infrequent events included intracranial hemorrhage (0.3%) and severe bradycardia requiring pacemaker insertion (0.9%) [33]. The most important adverse effect associated with the use of ticagrelor is bleeding. The risk of spontaneous bleeding with ticagrelor is 2.8% [32]. However, such bleeding prevalence occurred in the setting of a long-term (12 months) trial, while our study is limited to a single loading dose, thus reducing the risk of any side effect, in particular bleeding complications.

All clinical events described above, if they were to occur, as well as death, myocardial infarction, stroke, and urgent revascularization procedure with PCI or coronary artery bypass grafting will be recorded. Bleeding data will be collected using BARC definitions [34]. Clinical events will be evaluated by a local committee, comprised of 2 faculty members (2 cardiologists), not directly involved in the research. In the event of a report of a serious adverse event the local

committee will meet and antiplatelet treatment management will be managed according to physician recommendation.

Conflict of Interest

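### Randomising 20 patients with the plan's own 25% attrition leaves 15 expected evaluable patients, one short of the 16 behind the stated power (minor)

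*Combined protocol and SAP*

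**What the plan says.** The combined protocol and SAP, under Study endpoints, sample size calculation and statistical analysis, says that "a sample size of 16 patients will allow for the 95% CI to stay within ± 45 PRU with a 95% power and alpha=0.05". The next sentence makes the allowance for losses: "Considering a 25% data attrition rate due to hemolysis, drop out or technical problems, 20 patients will need to be randomized". The stated purpose is completeness: "20 patients will need to be randomized in order to ensure complete available data for analysis".

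The enrolment plan under Publication Strategy/Additional Information carries the same total: "complete enrollment in 8 months (total: 20 subjects" randomised.

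The document shows no inflation formula, has no rule for replacing patients who are lost, and does not say that the 25% is a percentage of the 16.

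**The concern.** An attrition allowance exists to protect the evaluable number on which the power was computed. Here the three printed figures (16 evaluable, 25% lost, 20 randomised) do not fit together on the ordinary meaning of an attrition rate, which is the share of those randomised who yield no usable data. On the plan's own assumption the trial should expect to finish below the number that supports its stated power. Any reader can see the mismatch from two consecutive sentences. What is at stake is a small loss of power and a sample-size statement that is wrong as written.

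**Working it through.** **Inputs**

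- From the sample-size paragraph: 16 evaluable patients, 25% attrition, 20 randomised, margin 45 PRU, true difference 0, SD 75 PRU, 95% power.
- From the statistical analysis text: a two-sided 95% confidence interval, that is, one-sided 0.025 for non-inferiority.
- From the design section: a two-period cross-over, so each complete patient contributes one paired difference.

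**Reproducing the plan's figure**

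- n × (1 + d) = 16 × 1.25 = 20. This matches exactly, so it is the likely route.

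**Checking what 20 delivers**

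- Expected evaluable: N × (1 − d) = 20 × 0.75 = 15.
- Randomised number needed for 16 at 25% loss: n/(1 − d) = 16/0.75 = 21.33, rounded up to 22. Then 22 × 0.75 = 16.5.
- Largest attrition at which 20 still yields 16: 1 − 16/20 = 20%.

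**Chance of reaching 16** (assumption: each patient is lost independently with probability 0.25)

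| Randomised | P(at least 16 evaluable) |
|---|---|
| 20 | 0.415 |
| 22 | 0.699 |

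With 20 randomised, falling short of 16 is more likely than not.

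**Effect on power**

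Power comes from a t distribution with n − 2 degrees of freedom, true difference 0 and margin 45. For one-sided non-inferiority the noncentrality is 45√n/SD, where SD is that of the within-patient difference. The documents give no such SD, so I solved for the value that makes the plan's 95% true at n = 16 and then evaluated power at n = 15.

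| Criterion | Back-solved SD of difference | Power, n = 16 | Power, n = 15 | Loss |
|---|---|---|---|---|
| Upper limit below 45 | 46.4 PRU | 95.0% | 93.4% | 1.6 points |
| Both limits within ±45 | 42.6 PRU | 95.0% | 93.0% | 2.0 points |

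For the first row the noncentrality is 45 × 4/46.4 = 3.88 at n = 16 and 45 × √15/46.4 = 3.76 at n = 15. The critical values are 2.145 (14 df) and 2.160 (13 df).

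For range, if the printed 75 PRU is taken as the SD of the paired difference, the one-sided calculation gives 60.8% at n = 16 and 57.6% at n = 15. The loss is then about 3 points, from a base far below 95%.

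**The case against.** Four points can be made on the other side.

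- **The 25% may be an allowance added to 16.** On that reading 20 is exactly right. But the text calls it an attrition rate and attributes it to haemolysis, drop-out and technical failure. Those losses fall on patients who have been enrolled, and nothing in the document defines the rate as an add-on. If that was the intention, the sentence still needs to say so.
- **Lost data need not mean a lost patient.** Haemolysis and technical problems can spoil one sample, and the planned mixed model can keep a patient with one usable period. This caveat stands: 15 is the expected number of complete patients, not necessarily the number in the model. It has limited force, because the plan sizes for complete data and a patient with one period adds little to a within-patient comparison.
- **The power loss is hypothetical.** This is true. The SDs of 46.4 and 42.6 PRU are back-solved, and the only printed SD, 75 PRU, does not reproduce 95% at n = 16 as the SD of the difference. The power figures illustrate the cost of one patient and should not be quoted as the trial's power.
- **Going to 22 does not ensure 16 either.** This is also true: the chance is about 70% under independent losses, and 22 is useful only if 16 is a sound base.

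None of these reconciles 16, 25% and 20 on the ordinary reading.

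**Conclusion.** The concern holds and is minor. With 20 randomised and 25% of them lost, the expected number of evaluable patients is 15, one below the stated 16. That conclusion needs only the printed figures and the usual definition of attrition as a share of those randomised. The accompanying power loss, about 1.6 to 2.0 points, further assumes that the plan's 95% at 16 patients is correct. How the 20 was reached is an inference from 16 × 1.25. No endpoint, margin or analysis model is affected. Whether 16 itself follows from the stated inputs is a separate and larger matter that this correction does not settle.

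**What to change.** In the sample-size paragraph, keep 20 randomised and 25% attrition, state that 15 evaluable patients are expected, and replace the power statement with the value for 15. Print the SD of the within-patient difference used for it, since power cannot be recomputed without that figure. It would also help to say whether an evaluable patient means one with usable PRU data in both periods.

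The cost is a short wording change and no extra patients; the enrolment section can stay as it is.

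There are two alternatives, each with a condition. Attrition could be restated as 20%, which makes 20 and 16 agree, but only if the sponsor has data supporting that rate. Keeping both 25% and 16 would mean randomising 22, two more patients, with the enrolment section changed to match, and only if 16 is confirmed as the right base number.

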The Switching Antiplatelet Therapy-5 (SWAP-5) study will be a prospective, randomized, double-blind, placebo controlled, cross-over PK and PD investigation aimed to rule out a DDI when ticagrelor is administered prior to cangrelor infusion. Aspirin treated patients with known coronary artery disease will be considered eligible for the study. The study will be performed at the Division of Cardiology of University of Florida Health, Jacksonville, Florida. Patients will be screened by Cardiology Research staff, who will verify that all candidates meet inclusion and exclusion criteria, and obtain their written informed consent to participate in the study. Results from blood tests performed within the last 90 days will be considered valid for screening purposes. If these are not available, a blood sample will be collected for the screening phase.

Using a computer-based randomization system, patients will be randomized in a 1:1 fashion to one of the following treatment arms: a) ticagrelor loading dose followed after 1 hour by cangrelor bolus and infusion or b) ticagrelor loading followed after 1 hour by placebo infusion. In line with FDA recommendations, ticagrelor will be administered as a 180mg loading dose (two 90mg tablets) [23]. Cangrelor will be used at the FDA recommended dose using a 30 μ g/kg bolus followed by 4 μ g/kg/min infusion [19]. The duration of cangrelor/placebo infusion

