will be 2 hours. After completing the first phase of the study, patients will undergo a 1-4 week wash-out period and then will cross-over to the alternative treatment in the second phase (i.e., patients assigned to treatment with cangrelor in the first phase will be assigned to placebo in the second phase and vice-versa). All patients will be on a background of aspirin therapy (81 mg daily maintenance dose). During each phase, PK and PD assessments will be conducted at 7 time points (total 14 time points): baseline (prior to ticagrelor loading dose; time -1 h); at start of cangrelor/placebo bolus and infusion (1 hour after ticagrelor loading dose); 30 minutes after cangrelor/placebo bolus; 1 hour after cangrelor/placebo bolus, 2 hours after cangrelor/placebo bolus (time of infusion discontinuation); 1 hour after discontinuation of cangrelor/placebo infusion; and 2 hours after discontinuation of cangrelor/placebo infusion. Figure 1 illustrates the overall study design. The study will have a double-blind design. Patients, research staff and laboratory personnel will be blinded to treatment assignments. Masking and randomization of medications (cangrelor and placebo) will be performed by our institutional research pharmacy in line with prior investigations [18].

Figure 1. Overall study design

Study Population

Inclusion criteria:

- Patients with known coronary artery disease (defined as prior type I myocardial infarction, coronary revascularization, percutaneous or surgical, or presence of at least a 50% stenosis in any major epicardial vessel).
- Age > 18 years old
- On aspirin 81mg/qd for at least 1 month

Exclusion criteria:

- Inability to provide written informed consent
- Hemodynamic instability
- On treatment with a P2Y₁₂ receptor antagonist (ticlopidine, clopidogrel, prasugrel, ticagrelor) in past 30 days
- Known allergies to ticagrelor or cangrelor
- Considered at high risk for bleeding
- History of intracranial bleeding/hemorrhagic stroke
- On treatment with oral anticoagulant (Vitamin K antagonists, dabigatran, rivaroxaban, apixaban, edoxaban) within past 30 days
- Known platelet count <80x10⁶/mL
- Known hemoglobin <10 g/dL
- Active bleeding
- Known end stage renal disease on hemodialysis
- Known severe hepatic dysfunction
- Acute or severe bronchial asthma or upper airway obstruction.
- Patients with sick sinus syndrome (SSS) or high degree AV block without pacemaker protection.

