Conformity to the normal distribution will be evaluated for continuous variables with the Kolmogorov-Smirnov test. For baseline characteristics, continuous variables will be expressed as mean \pm SD or median [IQR]. Treatment effects will be evaluated comparing the functional parameters observed in the overall patient population after cangrelor treatment with those achieved after placebo regardless of the sequence. All statistical comparisons of platelet function for the primary end point and exploratory end points with continuous variables will be conducted using a linear mixed-effect model with treatment group, sequence, period, and treatment-group-by-period as fixed effects, patient as a random effect, and baseline value of the corresponding

platelet function test as a covariate. The comparisons of rates of HPR will be conducted using the McNemar test.

Platelet reactivity results will be reported as least-square means (LSM) (95% confidence interval [CI]) for the above detailed analyses. LSM differences in PRU between groups and the corresponding 2-sided 95% CI for the difference will be obtained to assess non-inferiority based on the linear model. Given the exploratory nature of comparisons for secondary end points, correction for multiple comparisons will not be performed. A 2-tailed p value of <0.05 will be considered to indicate a statistically significant difference for superiority for all the analyses performed. Statistical analysis will be performed using SPSS version 25.0 software (SPSS Inc., Chicago, Illinois).

The safety population will include all randomized patients exposed to study medication. The PD population will include all patients with PD data and without a major protocol deviation thought to affect significantly the PD and PK of cangrelor or ticagrelor. The PD population will be used for analysis of all primary and secondary end points. Erroneously treated patients (eg, those randomized to one treatment but actually given the other) will be accounted for based on the actual treatment received.

Publication Strategy/Additional Information

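### Should the primary model adjust for PRU at the start of the infusion instead of the pre-ticagrelor value?

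*Combined protocol and SAP*

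**What the plan says.** Under Study design, each phase has seven sampling times. The first is "baseline (prior to ticagrelor loading dose; time -1 h"), the only sample called baseline. The second is "at start of cangrelor/placebo bolus and infusion (1 hour after ticagrelor loading dose").

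Ticagrelor is given in both arms. The active arm is "ticagrelor loading dose followed after 1 hour by cangrelor bolus and infusion"; the other receives placebo in place of cangrelor. Order is random: "patients will be randomized in a 1:1 fashion to one of the following treatment arms", with crossover after a wash-out.

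Under Study endpoints, sample size calculation and statistical analysis, the primary endpoint is "PRU measured at 2 hours after discontinuation of cangrelor vs. placebo". The model is a "linear mixed-effect model with treatment group, sequence, period, and treatment-group-by-period as fixed effects", with "patient as a random effect, and baseline value of the corresponding" platelet function test as covariate. The covariate is therefore the pre-ticagrelor value. The start-of-infusion value has no role in the primary model, and no sensitivity analysis uses it.

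**The concern.** The arms are identical until the bolus, and the question is whether cangrelor alters ticagrelor's effect. A value taken before ticagrelor cannot show how quickly ticagrelor worked on that day. The start-of-infusion value can, and it is the last scheduled measurement before the arms diverge. In a crossover, stable differences between patients drop out, so variation between a patient's two periods is what drives the error. If ticagrelor happened to act more slowly in the cangrelor periods, the difference would predate cangrelor, yet it could look like an interaction; the reverse could hide one.

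With 16 evaluable patients such imbalances are not rare, and a sample already being drawn seems to offer a free gain in precision. If the standard deviation (SD) of 75 PRU is that of the paired difference, the gain would be welcome, because power is then well below the stated 95%.

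**Working it through.** **Inputs from the plan.** 16 evaluable patients, SD 75 PRU, margin 45 PRU, true difference 0, two-sided 95% CI. The endpoint falls 1 + 2 + 2 = 5 hours after the ticagrelor dose; the alternative covariate would be taken at 1 hour.

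**The plan's own figure.** If 75 is the SD of the paired difference, n = (75 × (1.960 + 1.645) / 45)² = 36.1, so 37 patients, not 16. Sixteen patients give 95% power only if the paired SD is about 47. That is a separate matter and does not decide this one; 75 serves below only as a scale.

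**Step 1: is there bias?** Onset variation arises before the bolus. Because order is randomized, it is independent of treatment. A mean difference in onset between periods is absorbed by the period term. Only patient-specific variation between periods remains, and its expected contribution to the treatment contrast is zero. A simulated crossover (n = 16, true difference 0, paired SD 75, 6,000 runs per setting) confirmed this. The mean estimate was within about 0.7 PRU of zero with either covariate (Monte Carlo error about 0.25), including with a 30 PRU shift between periods.

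**Step 2: is the noise outside the planned interval?** No. Onset variation is part of the residual variance from which the interval is built. With the pre-ticagrelor covariate the simulated standard error stayed near 19.5 PRU however much onset contributed.

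**Step 3: how much precision might be gained?** Let r be the correlation between the within-patient period difference in the covariate and that in the endpoint. The documents give no r. If the pre-ticagrelor value has r = 0, the half-width is t(0.975; 13 df) × 75 × √(1 − r²) / √16, with t = 2.160:

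| r at start of infusion | Half-width (PRU) | Ratio | Power |
|---|---|---|---|
| 0 | 40.5 | 1.00 | 60% |
| 0.2 | 39.7 | 0.98 | 62% |
| 0.3 | 38.6 | 0.95 | 64% |
| 0.5 | 35.1 | 0.87 | 73% |
| 0.6 | 32.4 | 0.80 | 79% |

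**Step 4: how much might be lost?** The pre-ticagrelor correlation is just as unknown. The width ratio is √[(1 − r₀²) / (1 − r₁²)], with r₀ for the start of infusion and r₁ for the pre-ticagrelor value:

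- r₀ = 0, r₁ = 0.2: 1.02
- r₀ = 0.2, r₁ = 0.4: √(0.96/0.84) = 1.07
- r₀ = 0, r₁ = 0.4: √(1/0.84) = 1.09
- r₀ = 0.2, r₁ = 0.5: √(0.96/0.75) = 1.13

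A loss of 2% is therefore not an upper bound.

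**Step 5: the planned model is not a paired-difference analysis.** A random-patient model with one covariate slope blends the between-patient and within-patient relations. If patients with a high value at 1 hour also tend to be high at 5 hours, the blended slope can be too steep for the within-patient contrast and add error. In a random-intercept simulation (n = 16, 1,500 runs, treatment-by-period term omitted, uninformative pre-ticagrelor covariate), a between-patient correlation of 0.8 changed the standard error by +8%, +3% and −2% at within-patient r of 0, 0.2 and 0.3. A between-patient correlation of 0.5 with within-patient r of 0.3 gave −6%. Over a wider set of assumptions, including an informative pre-ticagrelor value, the ratio ran from about 0.85 to 1.11.

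**Step 6: size of a chance imbalance.** With an assumed paired SD of 47 to 75 PRU at the start of infusion, the standard error of the mean difference is 47/4 = 11.75 to 75/4 = 18.75. An imbalance above 20 PRU then occurs in 2 × [1 − Φ(20/11.75)] = 9% to 2 × [1 − Φ(20/18.75)] = 29% of trials. With equal SDs at both times, only r × 20 reaches the endpoint: 4 PRU at r = 0.2, 6 at 0.3 and 10 at 0.5, against a margin of 45.

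**The case for a change.** The best case for the change is that it needs no extra samples, spends no extra degree of freedom if one covariate replaces the other, and uses the last value before the arms separate. If ticagrelor onset carries over strongly to 5 hours, the gain is real: at r = 0.5 the interval is 13% narrower and power at SD 75 rises from 60% to 73%. In a trial this small that is not trivial. The description of the covariate as uninformative about onset is also correct.

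What stands is that a start-of-infusion covariate would be a reasonable alternative or sensitivity analysis. What does not stand is that it is clearly better. The endpoint is four hours later than the proposed covariate, and nothing in the documents indicates a correlation of 0.5 rather than 0.2. The sample is scheduled at the start of the bolus and infusion, without a statement that it precedes the bolus, and the Background describes cangrelor's effect as immediate. A value drawn just after the bolus would be affected by treatment and unsuitable as a covariate. The pre-ticagrelor value carries no such doubt. Finally, the plan compares the arms at every sampling time as exploratory analyses, so an imbalance at the start of infusion would be seen.

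**Conclusion.** The concern does not hold. The plan uses a legitimate pre-treatment covariate in a randomized crossover, and the resulting estimate is unbiased, with an interval that already allows for variable ticagrelor onset. Swapping the covariate would affect precision only, in either direction: simulated standard errors ran from about 15% smaller to about 11% larger, depending on between- and within-patient correlations that had to be assumed. At within-patient correlations of 0.2 to 0.3, even the paired-difference calculation that favours the swap gives a gain of only 2% to 5% in interval width. The validity conclusion rests on randomized order and on ticagrelor being given identically in both arms, both of which the protocol specifies.

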cangrelor which warrants at least 60 minutes for complete wash-out of effects (thus not adequate to rule out a DDI), and 12.5% of patients had high platelet reactivity at this time point [20]. Moreover, in none of the above mentioned studies were pharmacokinetic (PK) assessments performed to characterize the impact, if any, of cangrelor on systemic levels of ticagrelor and its major metabolite (AR-C124910XX). Therefore, the lack of data to rule out a DDI between cangrelor and ticagrelor when the latter is administered prior to starting cangrelor infusion warrants dedicated prospective investigations. The need for such investigations is underscored by the relatively high prevalence of pretreatment with ticagrelor in acute settings [21,22]. Importantly, such acute settings represent desirable scenarios to use cangrelor. Of note, use of prehospital ticagrelor (i.e, pretreatment) in acute settings is endorsed by practice guidelines both in the United States and Europe [17]. Therefore, ruling out a DDI between cangrelor and ticagrelor when the latter is administered prior to starting cangrelor infusion would have important clinical implications for real-world practice. The methodological approach for this assessment should rely on comprehensive PD assessments aimed to evaluate levels of P2Y₁₂ receptor inhibition and thrombus formation, PK assessments to assess systemic levels of the drug/drug metabolite, and mechanistic assessments by measuring levels of P2Y₁₂ receptor gene expression. In particular, different levels of P2Y₁₂ receptor gene expression can modulate the PD effects of oral P2Y₁₂ receptor inhibitors at a given level of drug exposure defined by PK profiling.

STUDY AIM

The aim of this investigation is to rule out a DDI when ticagrelor is administered prior to cangrelor infusion. Comprehensive PK and PD assessments will be conducted to reach this study aim.

REASERCH PLAN

[figure not shown]
Study design

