4) Total Thrombus-Formation Analysis System (T-TAS): T-TAS is an automated microchip flow chamber system for the quantitative analysis of the thrombus formation process under blood flow conditions. T-TAS allows measurement of thrombus formation using the PL-chip (Diapharma, West Chester Township, OH) [27]. The PL-chip contains 25 capillary channels (width 40 μ m, depth 40 μ m) coated with type I collagen and is specifically designed for quantitative analysis of platelet thrombus formation, including platelet adhesion and aggregation, granule secretion, and thrombus growth in the absence of coagulation and fibrinolysis systems. In measurements using the PL-chip, a blood sample collected in a hirudin containing blood sampling tube. The platelet aggregates gradually increase in size and, in the process, occlude the capillary, resulting in an increase in flow pressure. In the present study, total platelet-derived thrombogenicity is expressed as the area under the flow pressure curve for the first 10 min for the PL-chip tested at a flow rate of 18 μ L/min (PL18-AUC10). Low PL18-AUC10 reflect reduced thrombus growth and rapid breakdown of the thrombus.

4) *Pharmacokinetic (PK) assay:* Determination of plasma concentration of ticagrelor and its active metabolite (AR-C124910XX) will be assessed from blood samples taken at the same time points of PD analysis as previously described [28]. Blood samples for measurement of drug concentrations will be drawn through the same cannula used for PD sampling. The blood will be taken into lithium heparin tubes and placed on ice until centrifugation (2800 rpm, 4°C, 10 min) within 30 min of sampling to collect the plasma, which will be transferred to plain polypropylene tubes and frozen upright at or below -20°C until analysis. For ticagrelor and its active metabolite, the area under the plasma concentration vs. time curve from time 0 to the last measurable concentration (AUC_{0-t}), maximum plasma concentration (C_{max}), and time to C_{max} (t_{max}) will be estimated.

5) *P2Y₁₂ gene receptor level expression:* Gene expression in platelets will be performed using standard protocols. In particular, purified platelets are dissolved in Trizol reagent (Invitrogen) and total RNA will be extracted using RNA minipres kit (Zymos research) according to manufacturer's protocol. P2Y₁₂ mRNA expression will be measured with real-time PCR using SYBR green and specific primers as previously described [29].

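### PK is meant to help rule out an interaction, but the only criterion that clearly covers it is a superiority p-value, which cannot show how large a fall in ticagrelor exposure has been excluded

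*Combined protocol and SAP*

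**What the plan says.** **Aim.** The Study Aim section reads "The aim of this investigation is to rule out a DDI when ticagrelor is administered prior to cangrelor infusion", followed by "Comprehensive PK and PD assessments will be conducted to reach this study aim". PK is therefore offered as part of the rule-out, alongside PD.

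**PK quantities.** The pharmacokinetic assay description covers ticagrelor and AR-C124910XX. It lists AUC0-t, then "maximum plasma concentration (C_{max}), and time to C_{max} (t_{max}) will be estimated". It defines no contrast between cangrelor and placebo.

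**Status.** The section on endpoints, sample size and statistical analysis says "All other end points will be considered exploratory and will include the comparisons of PD and PK parameters", with comparisons "between all treatment arms at each time points".

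**Model.** The mixed model is introduced for "All statistical comparisons of platelet function for the primary end point and exploratory end points with continuous variables", and it adjusts for the baseline value of the corresponding "platelet function test as a covariate".

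**Intervals.** Least-square means with 95% CIs are promised for platelet reactivity results. A CI for the treatment difference is promised only for PRU, where it is set against a 45 PRU margin.

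**Criterion.** The one rule that reaches every analysis is "A 2-tailed p value of <0.05 will be considered to indicate a statistically significant difference for superiority for all the analyses performed".

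**The concern.** A superiority test asks whether the data are inconsistent with no effect. A rule-out aim asks how large an effect the data are inconsistent with. The plan uses the second logic for PRU, where a confidence limit is compared with a margin. For PK it names only the first.

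In a study of 16 to 20 patients, a non-significant PK p-value can arise because exposure is unchanged or because the estimate is imprecise. Without an effect estimate and an interval, the reader cannot tell which. What is at stake is the contribution that PK makes to the stated aim. The primary test is not at stake.

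**Working it through.** **1. Which rules reach PK.** There is no PK figure in the documents to reproduce: no PK sample size, variance, margin or power. The check therefore starts with the text.

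| Element of the plan | Applies to PRU | Applies to PK |
|---|---|---|
| Confidence interval for the treatment difference | yes | not stated |
| Margin | 45 PRU | none |
| Least-square means with 95% CI | yes (platelet reactivity) | not stated |
| Mixed model | yes | ambiguous |
| Two-sided p<0.05 for superiority | yes | yes |

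The mixed-model entry is ambiguous because the sentence opens with platelet function but goes on to exploratory continuous endpoints. The covariate is a baseline platelet function test, and AUC0-t and Cmax have no such baseline. On either reading, no PK ratio or difference, scale or interval is named as the result to interpret.

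**2. What a non-significant result would leave open.** This step is an illustration.

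Inputs from the plan: 16 evaluable patients, 20 randomized, two-period cross-over, two-sided 0.05. Whether 16 follows from the PRU inputs is a separate question and is not used here.

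Assumed inputs, because the documents give none: within-patient CV of 20%, 30% or 40%; a true fall in exposure of 20% or 30%.

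Formulas, log scale:
- s_w = √ln(1 + CV²)
- SE of the log ratio = s_w·√(2/n), with n − 2 degrees of freedom
- Miss rate = 1 − power of the two-sided 0.05 test, from the noncentral t with noncentrality |ln(ratio)|/SE

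Worked case, n = 16, CV 30%, true ratio 0.80:
- s_w = √ln(1.09) = 0.2936
- SE = 0.2936 × √(2/16) = 0.1038
- Noncentrality = 0.2231/0.1038 = 2.15; critical t on 14 df = 2.145
- Miss rate = 0.483

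All cases (probability of p>0.05):

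| CV (assumed) | 20% fall, n=16 | 20% fall, n=20 | 30% fall, n=16 | 30% fall, n=20 |
|---|---|---|---|---|
| 20% | 16% | 8% | 0.3% | <0.1% |
| 30% | 48% | 38% | 11% | 5% |
| 40% | 67% | 59% | 32% | 21% |

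**3. What an interval would add.** At n = 16 and CV 30%, the 95% CI around an observed ratio of 1 is exp(±2.145 × 0.1038) = exp(±0.2226), or about 0.80 to 1.25. At CV 20% it is 0.86 to 1.16, and at CV 40% it is 0.75 to 1.34. The p-value would be non-significant in all three cases, but only the interval shows how much they differ in what they exclude.

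**The case against.** The strongest reply is that the decision on an interaction does not rest on PK. The Project Summary ties the worry to reduced or abolished antiplatelet effect. That is a PD outcome, and PRU has a non-inferiority design with a margin and an interval. PK is openly exploratory, and the Study Rationale speaks of characterizing any impact on systemic drug levels, which is close to descriptive. All of this stands, and it limits the weight of the point.

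A second reply is that the mixed-model sentence may already cover PK as an exploratory continuous endpoint. That is a possible reading. It would supply a model, but still no log scale, ratio or interval, and it would bring in a covariate that PK parameters do not have.

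A third reply is that the illustration rests wholly on assumed CVs and falls. That is correct. The miss rates run from under 0.1% to 67%, so they do not show that this trial's PK data will be uninformative. For large falls at a low CV the problem is small.

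Two stronger readings are tempting. A reader might infer that the sponsor will take p>0.05 on PK as proof of no interaction. The plan does not say so; it says only when a difference will be called significant. A reader might also infer that the trial's main conclusion is undermined. It is not, because PRU non-inferiority is judged on its own interval.

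Exploratory status removes the need for a PK margin or PK power. It does not remove the need to say how PK results offered toward a rule-out aim will be summarised.

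**Conclusion.** The point holds as a mismatch between the role given to PK in the Study Aim and the only criterion that clearly governs it. It is moderate: it should be corrected before unblinding, but it leaves the design, the sample size and the primary analysis as they are.

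The mismatch itself is established from the text. Its practical size is not, because it depends on a within-patient CV and a relevant fall that the documents do not give. On the assumed inputs with 16 patients, a 20% fall would be missed about half the time at a CV of 30%, and much less often at a CV of 20%.

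**What to change.** Add to the statistical section:

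- For ticagrelor and AR-C124910XX, analyse ln(AUC0-t) and ln(Cmax) in a cross-over model with treatment, sequence and period as fixed effects, patient as a random effect, and no platelet-function covariate.
- Report the cangrelor/placebo geometric mean ratio with its confidence interval as the basis for interpreting PK. A 95% interval matches the rest of the plan; 90% would also serve.
- Define time 0 for the AUC. The Study Design section labels the sample before the ticagrelor dose as −1 h, so time 0 could mean the ticagrelor dose or the start of infusion. If it is the dose, the AUC includes an hour before any cangrelor.
- Report concentrations after the start of infusion as description. Treat the sample at the start of infusion as a check on comparability, not as a treatment effect.
- State that p>0.05 is not evidence of no interaction, and that PK is supportive estimation unless a justified no-effect range is pre-specified.

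**Cost.** SAP wording and a small analysis of data already planned, with no extra patients or samples. The downside is that the interval may be wide and inconclusive: about 0.80 to 1.25 around a ratio of 1 with 16 patients at an assumed CV of 30%.
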